## Randomization and Sample Size

Veterans were randomized to BBTI or CBTI in a 1:1 manner, in random block sizes of 2, 4, or 6, stratified by age (18-64 or ≥65) and use of a prescription sedative-hypnotic medication (yes or no). Sequentially numbered envelopes were used to assign participants based on their strata with concealment until randomization. Participants were enrolled by the Principal Investigator with the randomization strategy developed by the study statistician using Stata v14 and group assignment by the study coordinator.

Sample size was calculated based on non-inferiority methods (Julious, 2004) and was further informed by the calculation of a non-inferiority margin (NIM), the pre-specified difference between treatments that demonstrates BBTI is not unacceptably worse than CBTI (Schumi & Wittes, 2011). The Reliable Change Index (RCI; Jacobson & Truax, 1991; Sloan, Marx, Lee, & Resick, 2018) measures change at post-treatment not due to error, and for this study was calculated for the "control" condition (CBTI) using VA rollout data (Trockel et al., 2014). The RCI equation uses a measure of reliability (internal consistency or test-retest reliability) for the outcome measure, in this case the ISI. The RCI for CBTI was calculated using both reliability metrics to create a range of NIMs. Using Cronbach's alpha ( $\alpha$ =0.905; Morin, Belleville, Belanger, & Ivers, 2011) the RCI was 5.21 and using the test-retest reliability (r=0.78; Savard, Savard, Simard, & Ivers, 2005) the RCI was 3.43. We chose the NIM of 3.43. Accounting for 25% attrition, based on prior CBTI and BBTI studies (Buysse et al., 2011; Germain et al., 2014; Trockel et al., 2014) the target randomization goal was 56 participants (n=28/group) with 42 (n=21/group) completing post-treatment assessment to achieve 80% power.

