### **Statistical Analysis Plan**

Analyses were conducted with STATA v14. Baseline differences between CBTI and BBTI were analyzed using chi-square tests and t-tests.

To test treatment effectiveness, an intent-to-treat (ITT, n=63) and per-protocol (PP, n=24) approach were used. Consistent with ITT, all individuals randomized, regardless of their completion status, were encouraged to complete the post-treatment and follow-up assessments.

PP analyses were conducted on Veterans in each group that met strict criteria—attending all treatment sessions within the time frame defined *a priori* (BBTI: n=12, 4 sessions in 5 weeks; CBTI: n=12, 5 sessions in 8 weeks) and completing the one-week post-treatment assessment.

Linear mixed models (LMM) were used to test the main effects of treatment (CBTI vs. BBTI), time (baseline vs. post-treatment), and the interaction of treatment X time. Effect sizes were computed using Glass's  $\Delta$  ( $|M_{pre} - M_{post}|/SD_{pre}$ ; Morris, 2008).

Treatment response was an ISI reduction at post-treatment of  $\geq 8$  points (indicating a moderate response), and remission was a treatment response plus an ISI score  $\leq 7$  at post-treatment (indicating no clinically significant insomnia symptoms; Morin et al., 2011).

To establish BBTI as non-inferior to CBTI, the upper bound of the 95% confidence interval of the mean  $\Delta$ ISI from pre- to post-treatment ( $\Delta$ ISICBTI –  $\Delta$ ISIBBTI) cannot exceed the NIM of 3.43. If the upper bound of the confidence interval exceeds the NIM, non-inferiority cannot be declared (inconclusive). If the lower bound of the confidence interval exceeds the NIM, BBTI will be declared inferior to CBTI. However, should the upper bound of the confidence interval not exceed zero, BBTI will be declared superior to CBTI (Aberegg, Hersh, & Samore, 2018).

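### Allocation is stratified by age group and sedative-hypnotic use, but neither factor enters the stated analysis; if they predict ISI change, the non-inferiority interval is wider than the design warrants

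*Combined protocol and SAP*

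**What the plan says.** The Randomization and Sample Size section describes 1:1 allocation in random blocks of 2, 4 or 6, stratified by age (18-64 or ≥65) and by "use of a prescription sedative-hypnotic medication (yes or no"). The target is 56 randomised, with 42 (21 per group) "completing post-treatment assessment to achieve 80% power".

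The Statistical Analysis Plan says linear mixed models test "the main effects of treatment (CBTI vs. BBTI), time (baseline vs. post-treatment), and the interaction of treatment X time". The decision rule is separate: "To establish BBTI as non-inferior to CBTI, the upper bound of the 95% confidence interval of the mean" difference in ISI change must not exceed 3.43, and a bound above it is inconclusive. The plan does not say whether this interval comes from the mixed model or from a comparison of change scores. It adds that "an intent-to-treat (ITT, n=63) and per-protocol (PP, n=24) approach were used", and it defines the per-protocol groups by arm-specific rules ("BBTI: n=12, 4 sessions in 5 weeks; CBTI: n=12, 5 sessions in 8 weeks"). Age group and sedative-hypnotic use are not named in any analysis.

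**The concern.** Stratified allocation balances the two factors between arms, so their effect on ISI change contributes little to the true sampling error of the treatment contrast. An analysis without them still leaves that effect in the residual variance, so the reported standard error is too large. Non-inferiority turns on one upper bound against 3.43, so an interval wider than necessary costs power compared with an adjusted analysis.

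There is a second, smaller issue. The protection from stratification holds only while the strata stay balanced. The per-protocol set is selected after randomisation by different rules in each arm. In the ITT set, participants were encouraged to return "regardless of their completion status, were encouraged to complete the post-treatment and follow-up assessments", but loss could still differ by stratum and arm. In either case the unadjusted contrast can be biased.

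The model sentence may not be a full covariate list, and the documents do not say whether either factor predicts ISI change. The point is conditional on that.

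**Working it through.** **The plan's own figures.** The attrition step reproduces: 21/(1 - 0.25) = 28 per group and 42/0.75 = 56. The 21 per group cannot be checked because no SD of ISI change is given. With a true difference of 0, one-sided 0.025 and 80% power, it implies SD = 3.43/(2.8016 × √(2/21)) = 3.97. (At one-sided 0.05 it would be 4.47.)

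**Closed-form check.** Let R² be the share of ISI-change variance explained by the two factors; it is not in the documents and is taken here as 0 to 0.20. On change scores the half-width is t(0.975, df) × SD × √(1 - R²) × √(4/N), with the √(1 - R²) term only when adjusted.

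- N = 42, unadjusted (df 40): 2.47.
- N = 42, adjusted (df 38): 2.48, 2.42, 2.35, 2.22 at R² = 0, 0.05, 0.10, 0.20.

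With exact balance, unadjusted power is Φ[(2.8016 - 1.96)/√(1 - R²)] and adjusted power is Φ[2.8016/√(1 - R²) - 1.96]. At R² = 0.05, 0.10, 0.20 this gives 0.806 against 0.820, 0.813 against 0.840, and 0.827 against 0.879. The unadjusted one-sided error is Φ[-1.96/√(1 - R²)] = 0.022, 0.019, 0.014, so the omission is conservative here.

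**Simulation of the mixed model.** Allocation follows the plan's blocks in four strata. Assumptions: 30% aged ≥65, 40% on hypnotics, R² split equally between the factors, pre-post correlation 0.5, random loss from 56 to 42, and baseline-only participants kept. The model is a REML random-intercept model with 8,000 replicates per cell. Adjusted means both factors plus their interactions with time.

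| R² | Half-width, unadjusted | Half-width, adjusted | Change | Power, unadjusted | Power, adjusted | Error, unadjusted |
|---|---|---|---|---|---|---|
| 0 | 2.39 | 2.41 | +0.8% | 79.3% | 78.4% | 0.022 |
| 0.05 | 2.38 | 2.35 | -1.6% | 81.0% | 81.7% | 0.025 |
| 0.10 | 2.38 | 2.28 | -4.1% | 81.9% | 84.2% | 0.025 |
| 0.20 | 2.38 | 2.16 | -9.2% | 82.7% | 88.2% | 0.019 |

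With 63 randomised and an assumed 25% loss (47 with post-treatment ISI), the power changes are -0.5, +0.4, +2.5 and +4.8 points.

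**Form of adjustment.** Adding the factors as main effects only does not narrow the treatment-by-time interval: 2.39 against 2.39 at R² = 0, and 2.38 against 2.38 at 0.20. The factor-by-time terms are what matter.

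**Uneven loss, ITT (assumed).** Suppose 75% are retained overall, but hypnotic users make up about 45% of BBTI completers and 35% of CBTI completers, and hypnotic use carries all of R². At R² = 0.05, 0.10, 0.20 the unadjusted one-sided error is 0.036, 0.042, 0.041 if users improve more, and 0.014, 0.011, 0.007 if they improve less. Adjusted, it is 0.020 to 0.028. At R² = 0.10 the unadjusted contrast is biased by about 0.3 ISI points and the adjusted one by 0.02 or less.

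**Per-protocol set, 12 per arm (assumed shares, users improving more).** At the same three R² values the unadjusted error is 0.034, 0.037, 0.043 with 45/35% users and 0.038, 0.055, 0.066 with 50/30%; adjusted it is 0.023 to 0.030. With users improving less, the unadjusted error at 50/30% is 0.015, 0.011, 0.008. At R² = 0.05 the half-width is 3.32 unadjusted and 3.41 to 3.50 adjusted.

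**The case against.** The strongest reply is that no error in the plan is shown. The unadjusted test is valid under random loss, and leaving the factors out does not take power below the plan's 80%. That stands, and it is why the point is optional.

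The plan is also written in the past tense ("Analyses were conducted with STATA v14"), with both analysis sets already counted. If outcomes have been analysed, the power gain can no longer be claimed, and what remains is a sensitivity analysis. That stands too.

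The larger gains need strong predictors. If hypnotic use carried all of R², users and non-users would differ in ISI change by 3.97 × √(R²/(0.4 × 0.6)) = 1.81, 2.56 and 3.62 points at R² = 0.05, 0.10 and 0.20. The last exceeds the margin itself, and nothing in the documents supports any of these values. Likewise, the inflated error rates come from constructed imbalances, and they reverse when users improve less. Both should be read as illustrations of range.

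Finally, the documents do not tie the non-inferiority interval to the mixed model. That is a fair criticism of the plan, but it does not remove the point. Change-score regression on completers gives nearly the same power changes (-0.9, +1.1, +2.4, +5.7 points), from a lower unadjusted base of 76.4% to 80.2%.

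**Conclusion.** The concern holds as a minor, conditional efficiency point. Two factors used to stratify allocation are absent from every stated analysis. Under random loss at the planned size, adjustment costs 0.9 power points if they are irrelevant, gains about 2 points if they explain 10% of the variance in ISI change, and gains between 5 and 6 points at 20%. The loss is relative to an adjusted analysis, not to the planned 80%. Protection against false non-inferiority is not compromised while strata stay balanced and loss is random. It is not guaranteed in the per-protocol set, or in the ITT set if loss differs by stratum and arm, and the direction there is unknown.

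The sizes rest on the back-solved SD of 3.97 and on assumed values for R², the factor prevalences and the imbalances. The power gain is insensitive to the pre-post correlation: at 0.3 and 0.7 it stays within -0.7 to +5.8 points over the same R² range.

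**What to change.** State in the Statistical Analysis Plan that the ITT non-inferiority interval is the treatment-by-time contrast from the mixed model including age stratum and baseline prescription sedative-hypnotic use, each with its interaction with time. Report the unadjusted interval beside it. Main effects alone would achieve nothing.

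If outcome data have already been analysed, keep the unadjusted interval as the deciding one and label the adjusted interval a post hoc sensitivity analysis. Its purpose is then to check for stratum imbalance, not to gain power. In the per-protocol set (n=24), keep the unadjusted interval as the main result in either case and show the adjusted one only as a check: at R² = 0.05 it is about 3% to 5% wider (3.41/3.32 and 3.50/3.32).

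The cost is two sentences and one extra analysis. No new data are needed, since both factors were recorded for randomisation. The adjustment uses about two degrees of freedom on the change contrast. If the factors are irrelevant, the ITT interval widens by 0.7% to 0.8% and power falls by 0.5 to 0.9 points.

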#### **Procedures**

All study procedures took place at VA Pittsburgh Healthcare System (VAPHS); recruitment, treatment, post-treatment, and 3-month follow-up took place May 2016 through June 2019, with 12-month follow-up through March 2020. Participants were recruited with advertisements, by invitation from practicing insomnia providers, and with postings on Craigslist.com.

Eligible Veterans, after a brief phone or in-person screen, were invited for an in-person appointment to sign informed consent and complete diagnostic interviews and self-report measures. Assessment of insomnia and other sleep disorders was conducted using the South Texas Research Organizational Network Guiding Studies on Trauma and Resilience (STRONG STAR) Clinical Interview for DSM-5 Sleep-Wake Disorders (Taylor et al., 2018). Risk for obstructive sleep apnea (OSA) was assessed using the STOP-BANG questionnaire (Chung et al., 2012); Veterans scoring ≥5 and/or had untreated OSA were excluded and referred to the Sleep Medicine Clinic. Cognitive impairment was assessed using the St. Louis University Mental Status Examination (SLUMS; Tariq, Tumosa, Chibnall, Perry 3rd, & Morley, 2006); Veterans with scores ≤20, indicative of serious cognitive impairment, were excluded. Finally,

psychiatric disorders were assessed using the Structured Clinical Interview for DSM-5, Research Version (SCID-5-RV; First et al., 2015).

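### Does the decision rule need a separate verdict for BBTI being significantly worse than CBTI?

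*Combined protocol and SAP*

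**What the plan says.** The rule is in the last paragraph of the Statistical Analysis Plan section. The contrast is the ISI change under CBTI minus the ISI change under BBTI. The text does not give the sign of the change. The rule is coherent only if change means reduction, so that positive values count against BBTI, and I read it that way.

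Four verdicts follow:

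- **Non-inferior:** "the upper bound of the 95% confidence interval of the mean" change "cannot exceed the NIM of 3.43".
- **Inconclusive:** "If the upper bound of the confidence interval exceeds the NIM, non-inferiority cannot be declared (inconclusive").
- **Inferior:** "If the lower bound of the confidence interval exceeds the NIM, BBTI will be declared inferior to CBTI".
- **Superior:** "should the upper bound of the confidence interval not exceed zero, BBTI will be declared superior to CBTI".

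The same section plans a linear mixed model with a treatment-by-time interaction and attaches no verdict to it. It also states that "an intent-to-treat (ITT, n=63) and per-protocol (PP, n=24) approach were used".

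**The concern.** Superiority is judged against zero and inferiority against 3.43. A 95% interval of (−4.5, −0.5) is declared superior, while its mirror image (0.5, 4.5) is declared inconclusive. That is the word also given to (−1, 4.5), which includes zero. A reader who sees only the verdict could not tell a trial with too little information from one that showed BBTI to be significantly worse. CBTI is the established treatment here, so a demonstrated loss of efficacy against it should not be hidden behind a neutral word. Since the plan already tests against zero in BBTI's favour, it seems one-sided not to name the opposite result.

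**Working it through.** **Step 1: intervals and verdicts.** Applying the four sentences as written:

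| 95% interval, CBTI − BBTI | Verdict | Significantly worse than CBTI? |
|---|---|---|
| (−3, −0.5) | superior | no |
| (−1, 2) | non-inferior | no |
| (−1, 4.5) | inconclusive | no |
| (0.5, 4.5) | inconclusive | yes |
| (4, 8) | inferior | yes |

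The fourth row is the case at issue. The last row also meets the wording of the inconclusive sentence, but the inferior sentence is the more specific and plainly governs.

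**Step 2: the plan's own figures.** Randomization and Sample Size gives 21 completers per group for 80% power at a margin of 3.43, with 25% attrition. The attrition step reproduces: 21 / 0.75 = 28 per group, 56 in all. The 21 cannot be reproduced, because neither the SD nor the sample-size alpha is stated. Solving for the SD at a true difference of zero:

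SD = 3.43 × √(21/2) / (z₁₋α + 0.842)

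- one-sided 0.025: 11.11 / 2.802 = 3.97
- one-sided 0.05: 11.11 / 2.486 = 4.47

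The exact noncentral-t solutions are 3.87 and 4.39. An SD of 6 is added as a less favourable assumption.

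**Step 3: width of the unlabelled region.** With SD 3.97 and 21 per group, SE = 3.97 × √(2/21) = 1.225, and the half-width is 1.96 × 1.225 = 2.40. The interval lies wholly above zero once the observed deficit exceeds 2.40. The inferior verdict needs more than 3.43 + 2.40 = 5.83. Observed deficits between 2.40 and 5.83 are therefore significant yet called inconclusive.

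**Step 4: how often.** For true deficit d, the probability is Φ((5.83 − d)/1.225) − Φ((2.40 − d)/1.225).

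- d = 0: 1.000 − 0.975 = 0.025
- d = 2.0: 0.999 − 0.628 = 0.371
- d = 3.43: 0.975 − 0.200 ≈ 0.77

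Simulation with an estimated SD and t-based intervals (1,000,000 trials per cell) agrees. The ranges cover SD 3.87 to 4.39, with SD 6 in brackets:

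| True deficit | 21 + 21 | PP, 12 + 12 | ITT 63, as 32 + 31 |
|---|---|---|---|
| 0 | about 2.5% | about 2.5% | about 2.5% |
| 1.0 | 11–13% (8%) | 8–9% (6%) | 14–17% (10%) |
| 2.0 | 30–37% (18%) | 18–23% (11%) | 43–52% (25%) |
| 3.43 | 67–78% (41%) | 42–52% (24%) | 84–91% (58%) |

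The ITT column assumes a 32/31 split and post-treatment data on all 63, although 25% attrition was planned for.

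**Step 5: could BBTI be called non-inferior while significantly worse?** The interval would have to fit between 0 and 3.43, so its half-width must be below 3.43 / 2 = 1.715. Expected half-widths are 2.41 to 2.74 (21 + 21), 3.28 to 3.72 (12 + 12) and 1.95 to 2.21 (32 + 31) for SD 3.87 to 4.39. Such intervals occur in at most 0.6% of simulated trials.

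**Step 6: what a new label would alter.** The non-inferiority test depends only on whether the upper bound exceeds 3.43. A label keyed to the lower bound changes neither that test, nor its error rate, nor any estimate.

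**The case for a change.** The strongest case for a change is that the plan does not confine itself to non-inferiority. It adds a verdict keyed to zero in the direction that favours BBTI and none in the other. At 21 per group, superior needs an observed advantage of about 2.4 to 2.7 points, whereas inferior needs an observed deficit above about 5.8 to 6.2. If BBTI is truly worse by the full margin, only 2.5% of trials are called inferior and 95% inconclusive. Of the latter, 71% to 82% have an interval wholly above zero (44% if the SD is 6). Naming that result would take one sentence.

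The asymmetry stands, and so do the figures. Three things limit what follows from them:

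- A verdict for a worse result does exist, set against the margin. The plan defines the margin as the boundary of unacceptable loss, so judging inferiority there is consistent with that definition.
- The parenthetical word qualifies the non-inferiority conclusion. An interval of (0.5, 4.5) leaves open whether the loss is larger than the margin, so the word is accurate.
- The large percentages require BBTI to be truly worse by about the margin. Under equal efficacy, the premise of the back-solved SD, the figure is about 2.5%.

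**Conclusion.** No change to the plan follows. The rule is silent on an interval lying wholly above zero, but that is a missing descriptive label and not a fault in the test. Followed as written, the plan makes no false claim of non-inferiority when the interval crosses 3.43. The verdict is read off an interval whose lower bound shows directly whether zero is excluded, and the treatment-by-time interaction tests the same between-arm difference in change. An analyst reporting such a result would say that BBTI did significantly worse and that non-inferiority was not shown; the two statements are compatible. The sign of the change is likewise settled by the only reading under which the rule works.

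At 21 per group the affected share is about 2.5% at no true difference, 18% to 37% at a true deficit of 2.0 and 41% to 78% at 3.43, for assumed SDs of 3.87 to 6. Those are frequencies of a wording, not of a wrong decision. Treatment and 3-month follow-up ran to June 2019, "with 12-month follow-up through March 2020", and the SAP is written in the past tense. A new verdict category would therefore be post hoc, with no gain in any result.
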